## **Background**

Interventions that engage adolescents living with HIV to improve adherence to antiretroviral therapy (ART) are urgently needed. Adolescents repeatedly demonstrate suboptimal levels of ART adherence, which is associated with increased morbidity and mortality. Developing adherence-promoting interventions for adolescents requires an understanding of factors that shape adherence from multiple levels. Developmental theories suggest that adolescents are particularly sensitive to their social networks. Mobile health (mHealth) interventions, those that use mobile technology (e.g., smartphones apps) to transmit health information, hold promise as an effective way to improve ART adherence. These smartphone apps can be used to engage social networks and provide social support. Access to mobile phone technology is rapidly increasing among youth in South Africa, making mHealth interventions feasible and potentially scalable in this setting. This study will adapt HealthMpowerment, a theory-based mHealth intervention developed in the U.S., to improve ART adherence among South African adolescents living with HIV. The adapted intervention is called *MASI* (*MA*sakhane *Siphucule Impilo Yethu*; isiXhosa for 'Let's empower each other and improve our health').

## **Purpose of the study**

The purpose of this study is to customize and pilot test an mHealth intervention to promote ART adherence among adolescents and young adults (AYA) living with HIV in Cape Town, South Africa. We will first analyze secondary data collected as part of the *Cape Town Adolescent Antiretroviral Cohort* to identify the relationship between social network-level factors and clinical outcomes (e.g., ART adherence and viral load) in this population. Next, we will conduct formative research, including multiple phases of in-depth interviews (IDIs), to iteratively adapt HealthMpowerment to create *MASI* for adolescents living with HIV in Cape Town. Finally, we will pilot test *MASI* with 50 AYA living with HIV to a) assess its feasibility and acceptability and b) explore preliminary effects on ART adherence and social support. Qualitative data collection will help identify and refine next steps for *MASI*.

## **Background on HealthMpowerment and *MASI***

HealthMpowerment is a theory-based intervention developed in the U.S. to engage HIV-positive, negative, and status-unknown youth and to reduce HIV-related risk behaviors. An earlier version of HealthMpowerment resulted in significant reductions in risky sexual behaviors among young men who have sex with men in the U.S. The app includes an anonymous social network. Participants have usernames and avatars, but no identifying information is included for each person. We advise all participants to pick a username that does not include their real name, email address, or their other social media account names. HealthMpowerment has now been updated for delivery via iOS and Android smartphones in a nationwide study in the U.S. that launched in July, 2020. For our study, *MASI* will support the following features:

- Forums - Start or add to existing discussions, upload images, videos; favorite posts and follow others; research staff (including peer mentors) monitor and add to forum posts to encourage dialogue
- Med Tracker - Track ART adherence in calendar; schedule tailored reminders for taking medicine
- Ask an Expert – Post/read questions answered by local doctors/counselors; posted anonymously
- Activities - Engaging activities including quizzes, self-assessments, and goal setting activities
- Resource Center - Multi-media resources and information on various health topics
- Gamification - Sophisticated tracking of app use to trigger tailored rewards; badges awarded

We will customize all of the intervention content so that it is relevant to adolescents in Cape Town.

## **Overview of the study procedures and participants**

The proposed study is nested in larger study titled "Improving Assessment for Neurocognitive Impairment among Perinatally HIV Infected Youth (*NASA study*)" (REF: 215/2018). The proposed research will address the following three specific aims.

### **Aim 1: Analysis of Secondary Data; previously approved by UCT HREC with IAA between UCT and Duke**

The first aim consists of secondary data analysis of data generated from adolescents living with HIV enrolled in the *Cape Town Adolescent Antiretroviral Cohort* (CTAAC; HREC: 051/2013; Amendment: 18

April 2017). After the approval of the of the Protocol Amendment, we established an IRB Authorization Agreement between UCT and Duke University for the analysis of these data (IAA; executed July 13, 2017).

The purpose of this aim is to identify the relationship between social network-level factors (including structural and functional characteristics of their social networks) and HIV-related clinical outcomes including ART adherence and viral suppression among adolescents living with HIV.

**Aim 2: Formative research to iteratively customize an mHealth intervention to promote ART adherence among adolescents living with HIV by engaging their social networks**

In this aim, we will collect data from adolescents to customize the HealthMpowerment app for this population. We will recruit participants from the larger NASA study. Participants and caregivers in the NASA study are regularly asked for assent/consent to be approached about additional research studies (documented on an ok-to-contact list), which we will use for recruitment into this study. Participants will be eligible to participate if they have daily access to an Android or iOS smartphone meeting minimal requirements (e.g., Operating system is Android version 5.0 or higher or iOS version 10 or higher, phone has at least 200 mb in free storage). Participants will be asked to participate in 1 in-depth interview (IDI), another set of 2 IDIs (before and immediately after beta testing the app), or both.

In the first phase of Aim 2, we will conduct IDIs with approximately 15 adolescents living with HIV (ages 14-20 years). After providing consent/assent, participants will be asked to complete a brief survey about their background; social support; stigma; adherence to treatment; and use of their smartphone for getting health information. The interviews will take about 1.5 hours and will include questions about experiences with HIV treatment; support and challenges related to ART adherence; how COVID-19 has impacted their care and treatment; use of phones generally and how phones are used to search for health information; what they want in a smartphone app designed to support adolescents living with HIV (e.g., what topics should be included in the app). The IDIs will also be an opportunity to explore potential risks and harms related to privacy, confidentiality, and unintended consequences (e.g., stigma and inadvertent disclosure). Interviews will be audiotaped and then translated and transcribed from Xhosa to English.

In the second phase of Aim 2, we will conduct app testing of our customized app. Study activities for this phase of Aim 2 will include a set of 2 IDIs with 12-16 adolescents living with HIV (ages 14-20 years). Prior to the first IDI, participants will be asked to complete a brief survey about information on their background; social support; stigma; adherence to treatment; and use of their smartphone for getting health information. The first IDI will take about 2 hours and will be about opinions about how the app and study logo look, opinions about how the avatars look and how to improve them, opinions about earning points and badges and how to make them more engaging. During the visit for the first IDI, we will install the app on each participant's phone. After the participant registers and creates a private username and password, we will demonstrate how to use the app. Participants will be asked to spend at least 10 minutes a day on the app for 1-3 weeks, until the second IDI is scheduled. We will be able to monitor where participants go within the app, what features/articles are used, and the length of time spent on the app. Participants will be given smartphone data to support their use of the app during this time. The second IDI, will allow participants to provide feedback based on their experience with the app, desired improvements, proposed changes to the community guidelines, and information on facilitators and barriers to uptake and daily engagement as well as any technical difficulties encountered, privacy or confidentiality concerns.

**Aim 3: Pilot test the mHealth intervention with 50 adolescents and young adults living with HIV to (a) assess its feasibility and acceptability and (b) explore preliminary effects on ART adherence and social support**

We will conduct a pilot randomized controlled trial (RCT) to test *MASi* with 50 AYA with HIV (25 males and 25 females). We will recruit participants from the larger NASA study using the same procedures used successfully in Aim 2. Additional participants will be recruited outside NASA at public ART clinics linked to Groote Schuur Hospital in Cape Town, South Africa, and through participant referral.

**Screening and participant eligibility:** Participants will be screened by phone to see if they meet the following eligibility criteria:

- Age >= 15 years and <= 21 years
- Knows HIV status (Screened AYA who do not know their HIV status will receive information on free voluntary HIV counseling and testing services)
- Living with HIV
- Has been prescribed medication to treat HIV
- Not attending school for learners with special needs (e.g., School of Skills)
- Has not repeated a grade in school more than once
- Have a smartphone that can download apps
- Feels comfortable using an app with content in English
- No plan to move outside of Cape Town in the next six months

- Have not previously participated in the MASi app testing phase of our study

Participants who meet these criteria will be invited for an in-person appointment. After completing the informed consent/assent process (including consent from an adult, if applicable), we will confirm the final eligibility criteria:

- Able to successfully install the MASi app on their smartphone

Eligible participants will complete a baseline assessment, which will be an interviewer-administered survey with data entered electronically by the interviewer using REDCap data collection software. Paper surveys will be available in the event online data entry is not possible. For survey questions with a higher potential for social desirability bias (e.g., sexual behavior and study feedback), we may offer participants the opportunity to self-enter data into REDCap.

Following the baseline assessment, the interviewer will use REDCap's randomization tool to assign participants to condition. Using this process, participants will be randomized to the intervention or control condition (1:1), with randomization stratified by gender. The intervention condition will include all features of *MASi* while the control condition will be an information-only version of *MASi* which will include the Resources feature and homepage. Study participants will be asked to engage with the app for 6 months. All participants will receive 1G in monthly cellphone data packages for 6 months; research staff will touch base with participants each month to ensure the participant still has access to a working device before sending data.

Participants will complete follow-up assessments as well as 3- and 6-months follow-up. Assessments will take approximately 60 minutes and will be conducted in a private room so that participants can speak without being overheard. Phone assessments may be conducted in the event it is not possible to conduct in-person data collection. Assessments will include questions about assessing demographics, HIV-related knowledge, social support, loneliness, resilience, anxiety, depression, stigma, disclosure concerns, disclosure intentions, treatment adherence, sexual activity, perceived usability of *MASI*, and participant feedback about the study overall.

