day. If a participant posts something that could be considered in breach of the guidelines, study staff will remove the post and contact the participant to notify them and explain why the post was removed. Our protocol describes additional action steps should a participant accumulate three violations of this nature. Study staff will also monitor posts for content that indicates a need to implement the SOP for Various Scenarios, including concerns about harm to the participant or others.

*Unintended disclosure.* Unintended disclosure is also a potential risk. Study staff will be trained (or re-trained) on confidentiality standards and proper interviewing techniques to minimize this risk. Participant names will not be included in any data collection instruments or intervention forum posts. The only numbers used to label and identify data from the participant will be the Study ID or their username (app handle) for the intervention. Questionnaires and audio files will be linked using the Study ID and the interview date. We also have extensive data procedures already in place to ensure security of the data and information provided by participants. Data will not be released to non-study staff at any time. All electronic data sharing between sites will be done only on the secure server (e.g., via Duke Box.com).

*Privacy and confidentiality concerns.* Participants may have privacy and confidentiality concerns. Participants will be reminded to consider their surroundings and the privacy of their device before engaging with the intervention app. No communication between study staff and participants will include sensitive information about HIV or anything that could reveal their participation in a study. To protect their privacy, participants will be required to enter a PIN to gain access to the app if it has been 5 minutes since the app was open on their device, or 15 minutes if the app was open but inactive as a fail-safe to avoid unintended disclosure. Participants will also be encouraged to interact with the study application when in private. Participants in focus group discussions will be asked to respect confidentiality and not share the identities of other participants or content shared in the discussions. Finally, participants will be notified of these risks in the consent process.

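### Aim 3's phone screen offers HIV testing information to anyone who does not know their status, a rule that suits referred candidates but not NASA or ART-clinic candidates, who have most likely not been told

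*Combined protocol and SAP*

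**What the plan says.** Under Aim 3, Screening and participant eligibility, the protocol says "Participants will be screened by phone to see if they meet the following eligibility criteria". Ten criteria follow, and three are about HIV: knowing one's status, living with HIV, and "Has been prescribed medication to treat HIV". The first of these carries its own rule for a negative answer: "Knows HIV status (Screened AYA who do not know their HIV status will receive information on free voluntary HIV counseling and testing services".

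The order of events is then set out. "Participants who meet these criteria will be invited for an in-person appointment", and only there is consent taken: "After completing the informed consent/assent process (including consent from an adult, if applicable), we will confirm the final eligibility criteria". The single criterion left for that point is installing the app.

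There are three recruitment sources. The first is the NASA study, whose title in the Overview is "Improving Assessment for Neurocognitive Impairment among Perinatally HIV Infected Youth". The other two come in one sentence of Aim 3: "Additional participants will be recruited outside NASA at public ART clinics linked to Groote Schuur Hospital in Cape Town, South Africa, and through participant referral".

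The privacy paragraph of Protection against risks adds a general rule: "No communication between study staff and participants will include sensitive information about HIV or anything that could reveal their participation in a study".

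**The concern.** The HIV questions are put by phone to people aged 15 to 21 who have not yet consented. For those under 18, no caregiver has consented to the study either. One rule then covers every candidate who does not know their status, and it treats that person as untested. Two of the three sources, however, consist of young people identified through an HIV study or HIV treatment. If such a person does not know their status, the likely reason is that nobody has told them. A call from a study tied to that source, with questions about HIV and then testing information, could tell them, or tell someone within earshot.

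The protocol itself names unintended disclosure among its potential risks, and a disclosure cannot be taken back. A secondary effect is possible: a young person who cannot talk freely may deny HIV or its treatment and be screened out. That would thin out those with the least privacy in a pilot whose main purpose is feasibility and acceptability. The documents give no means of judging how often this would happen.

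**Working it through.** No figure in the plan is at issue. The sample of 50 is justified in the SAP by feasibility and budget, with no power inputs. The check is therefore a comparison of texts.

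**Step 1: what is asked by phone, and when.** The phone list has ten items: age, knowing status, living with HIV, HIV medication, type of school, grades repeated, smartphone, comfort with English, plans to move, and earlier app testing. Three of the ten are HIV items. All ten precede the in-person appointment, and consent or assent is taken at that appointment. So the HIV items come before consent as the protocol describes it.

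**Step 2: what not knowing means, by source.**

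| Source | What the documents say of it | Likely meaning of not knowing | Does testing information fit? |
|---|---|---|---|
| NASA | Titled as a study of perinatally infected youth (Overview) | Infected, not told | No |
| Public ART clinics | Clinics that provide HIV treatment (Aim 3) | In care, not told | No |
| Participant referral | No HIV status implied (Aim 3) | May be untested | Yes |

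The first two rows assume that NASA candidates are infected, as the title indicates, and that clinic candidates are patients there. The same answer has different meanings across the rows, while the protocol has one response to it.

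**Step 3: which safeguards reach the call.**

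- Protection against risks covers staff training in confidentiality and interviewing, labelling of data by study ID or username, secure data sharing, the app PIN, and reminders about surroundings when using the app.
- Confidentiality covers private study visits and the content of messages.
- Aim 3 provides a private room for assessments.
- Aim 2 describes the list of NASA participants and caregivers who have agreed to be approached about further research, and Aim 3 reuses those recruitment procedures.

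The training is general and could extend to calls. The NASA list gives permission for contact. Nothing says who may be spoken to, whether the person can talk in private, or in what order the HIV items are put. No permission equivalent to the NASA list is described for clinic or referred candidates.

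**Step 4: scope of the communication rule.** Read literally, the rule forbids the HIV items on the call. It would equally forbid the consent discussion, the baseline interview, and the 3- and 6-month assessments of adherence and stigma, which Aim 3 allows by phone. That cannot be intended. The sentence stands among safeguards for devices and the app, and Confidentiality has a similar rule for messages, so outgoing messages are the likely target. The wording does not say so.

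**Step 5: frequency.** The documents give neither the number screened nor the share not told. Purely as an assumption, 1% of 80 is 0.01 × 80 = 0.8 people, and 5% of 100 is 0.05 × 100 = 5. Nothing in the documents supports those inputs or excludes zero, and the misfit concerns only the candidates from NASA and the clinics. The conclusion does not use this range.

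**The case against.** The strongest reply is that the documents show an omission and not a harm. No phone script is reproduced. Knowing one's status is listed first among the HIV items, so if the call follows the list, someone who answers no can leave before the other two are asked. Testing information is what any untested person would be given. Staff are trained in confidentiality, NASA families have agreed to be approached, and the rule fits referrals. All of this stands, and it limits the point. It does not remove the misfit for NASA and clinic candidates, because the rule as written sends them testing information whatever order is used. The protocol refers to an appended procedure for various scenarios, which is not available here, but the use described for it is potential harm and legal reporting.

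Three stronger readings are tempting and are not supported:

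- A reader might infer that a site cannot obey both the phone screen and the communication rule. Step 4 shows that the literal reading would also stop the study's own consent talks and assessments. This is unclear scope, not an impossible instruction.
- A reader might infer that all candidates are called without any permission. For NASA that is wrong.
- A reader might conclude that the HIV criteria belong after consent. A referred candidate who is untested or untold would then be taken through consent for an HIV adherence study, including a check that they can recall its purpose, before anyone asked whether they know their status. That could cause the disclosure it was meant to prevent.

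**Conclusion.** The point holds in limited form. The HIV criteria are asked by phone before consent, and the rule for those who do not know their status does not fit two of the three recruitment sources. For those two, following the rule misdirects an adolescent who has not been told, and the call could disclose the diagnosis. That disclosure is a reasonable inference and not something the documents record. It rests on the two assumptions in Step 2 and on there being no unseen script that already deals with the matter. Its frequency is unknown and may be zero.

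The issue is one of participant safety and procedure. No sample size, randomisation or analysis changes. It merits action because the harm could not be undone and the main remedy is small. The privacy check on the call and the scope of the communication rule are clarifications that would not justify an amendment on their own.

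**What to change.** 1. For NASA and ART-clinic recruits, have the NASA or clinic staff who already hold the record put forward only young people confirmed to know their HIV status, before any study call. State the permission on which clinic candidates are put forward, since the protocol describes one only for NASA.
2. Limit the testing-information rule to candidates who come by participant referral.
3. Open every screening call with a check that the right person is on the line and can speak privately. Ask about knowing one's status before the other HIV items, and stop those items if the answer is no.
4. Reconcile the communication rule in Protection against risks with the phone screen and the phone assessments in Aim 3 by stating whether it covers outgoing messages only.
5. Reconcile the handling of a NASA or clinic candidate who nevertheless turns out not to know their status with the sponsor's own disclosure procedures. This review does not propose what those should be.
6. Leave the HIV criteria before consent.

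The cost is rewording of Aim 3 and one sentence in Protection against risks, a short record check by existing staff, and possibly a few candidates who are not put forward.

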## Statistical Analysis Plan

The study will enroll 50 adolescents and young adults with HIV into the study (25 males and 25 females based on self-reported sex assigned at birth). The study's sample size ( $n = 50$ ) was selected to be large enough to reasonably evaluate the feasibility and acceptability of MASi while balancing budgetary constraints.

Descriptive summaries will be computed for all study outcomes with continuous variables summarized with means and standard deviations (or medians with interquartile range in the case of skewed distribution) and categorical variables summarized with counts and proportions. Outcomes will be summarized, stratified by treatment group, at each available study time point.

As a pilot study with a primary focus on feasibility and acceptability, the examination of MASi's preliminary efficacy will be exploratory. To explore MASi's preliminary efficacy on ART adherence and social support at 3- and 6-months, we will use linear mixed models to compare outcomes among participants randomized to MASi compared vs. the information-only control at each time point. Log transformed outcomes and alternative modeling approaches such as Poisson and negative binomial will be considered in the event that assumptions for the linear model are violated. All models will include a fixed effect for sex assigned at birth (stratification variable) and a random intercept term to account for correlation in the response due to repeated measures within study participants over time. A random slope for participant will also be considered, as will the covariance structure of the errors (e.g., exchangeable, autoregressive). Distribution of residuals will be examined to confirm that modeling assumptions are met. Because sample size is small (this study is not powered to detect clinically meaningful effect sizes) and the regression analyses are exploratory in nature, inference will focus on the size and direction of the total treatment effects rather than statistical significance.

Additional exploratory analyses will examine MASi's effects over time on HIV/AIDS knowledge and stigma using methods similar to those employed for adherence and social support outcomes. We will also conduct descriptive analyses examining trends and patterns in user engagement with various components of the MASi interface over time.

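### Does it matter that randomisation is stratified by gender while the models adjust for sex assigned at birth?

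*Combined protocol and SAP*

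**What the plan says.** The randomisation text in the Aim 3 section states that "the interviewer will use REDCap's randomization tool to assign participants to condition" and that "participants will be randomized to the intervention or control condition (1:1), with randomization stratified by gender". It does not name the field or define gender. The opening of Aim 3 gives the enrolment target as 25 males and 25 females, with no further definition.

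The Statistical Analysis Plan is more specific. It describes the target as "25 males and 25 females based on self-reported sex assigned at birth". On the models it says: "All models will include a fixed effect for sex assigned at birth (stratification variable". It gives no power calculation: the sample size "was selected to be large enough to reasonably evaluate the feasibility and acceptability of MASi while balancing budgetary constraints". It also says that "the regression analyses are exploratory in nature" and that interpretation will rest on the size and direction of effects rather than on significance.

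**The concern.** An analysis should normally adjust for the factor used to stratify the randomisation. Stratifying makes the arms alike on that factor. A model that leaves it out, or replaces it with a near copy, leaves some outcome variation in the residual and tends to overstate the standard error. Gender and sex assigned at birth are different variables, and a SAP that specifies self-reported sex assigned at birth seems to have chosen its term with care. Read literally, the protocol stratifies on one and the SAP fits the other. A participant whose gender differs from sex at birth would then be placed in the wrong stratum in the model. Nothing in the documents states that the two terms mean the same field.

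What is at stake is the precision of the exploratory comparisons: adherence and social support at 3 and 6 months, and the similar models for HIV knowledge and stigma.

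**Working it through.** **The texts side by side**

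| Item | Protocol, Aim 3 | Statistical Analysis Plan |
|---|---|---|
| Quota | 25 males, 25 females, not defined further | 25 and 25 by self-reported sex assigned at birth |
| Stratum | gender, not defined | sex assigned at birth, labelled as the stratification variable |
| Model term | not covered | sex assigned at birth |

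The quota agrees in both places: 25 + 25 = 50. The SAP uses one variable for quota, stratum and model. The single word in the protocol is the only outlier, and it sits in a section whose own quota is in males and females.

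**What a real loss of precision would need**

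1. The REDCap field is gender, despite the SAP's label.
2. At least one of the 50 participants is discordant.
3. The outcome depends on gender rather than on sex. If it depended on sex, the SAP's model would be the better fit.

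The documents support none of the three.

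**Size if all three held**

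Inputs from the documents: n = 50, 25/25 by sex, 1:1 allocation. Assumptions, because the documents give no figures: 1 to 5 participants discordant; a gender effect *b* of 0.5 to 1.0 residual SD; residual SD 1; no treatment effect; one time point in place of the mixed model.

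With the correct stratum fitted, the standard error of the difference is about √(1/25 + 1/25) = 0.283. The simulated mean model SE is 0.281 to 0.282.

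With sex fitted instead, and a proportion *p* discordant, the residual variance grows from 1 to about 1 + b²p(1 − p). The SE is therefore multiplied by √(1 + b²p(1 − p)):

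- p = 1/50 = 0.02, b = 0.5: √(1 + 0.25 × 0.0196) = √1.0049 = 1.002
- p = 5/50 = 0.10, b = 1.0: √(1 + 1 × 0.09) = √1.09 = 1.044

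Simulation (40,000 runs per setting) gives the rise in mean model SE:

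| Discordant of 50 | b = 0.5 SD | b = 1.0 SD |
|---|---|---|
| 0 | 0% | 0% |
| 1 | 0.3% | 1.1% |
| 2 | 0.6% | 2.1% |
| 3 | 1.0% | 3.1% |
| 5 | 1.5% | 4.9% |

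In absolute terms the SE goes from 0.281 to 0.282 at the mild end (one discordant, 0.5 SD) and from 0.281 to 0.295 at the severe end (five discordant, 1.0 SD). The simulated values run slightly above the formula, which ignores the degrees of freedom and chance imbalance of the arms over sex.

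**Reported SE against true spread**

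The allocation is balanced on gender, so the gender part of the outcome nearly cancels between arms even when the model omits it. In the severe case the actual standard deviation of the estimate rises only from about 0.282 to 0.291: 0.291/0.282 = 1.03, or about 3%. The rest of the 4.9% is a slightly conservative reported SE, not lost precision.

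**Bias**

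Swapping the arm labels leaves the allocation probabilities unchanged, so with no treatment effect the mean estimate is zero whichever variable is fitted. The largest simulated mean was 0.0025 SD, with Monte Carlo standard error 0.0014.

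**The case for a change.** The best case for acting is traceability. Both sentences are current text, they describe the same object, and they name it differently. A programmer, or someone repeating the analysis, cannot tell from the documents alone which field REDCap used. The SAP clearly means to fit the randomisation stratum, so naming the field would make that checkable at almost no cost.

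The inconsistency stands: the two sentences do use different words. The inference that the models may therefore miss the randomised strata does not stand without further facts. The SAP already commits to fitting the stratification variable. An analyst can see in the REDCap randomisation set-up which field was used and fit that field, which is what the SAP intends. Aligning the words would be tidy, but it would not alter how the data are collected, allocated or interpreted.

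**Conclusion.** This is a clerical slip, and correcting it would bring no statistical gain. The likeliest position is that one male/female variable serves as quota, stratum and covariate, and that the protocol names it loosely. In that case the effect is nil.

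If the REDCap field were gender, the cost under the assumptions shown would run from about 0.3% in the standard error (one discordant participant, 0.5 SD) to about 3% in true spread and 4.9% in the reported SE (five of 50, 1.0 SD). The upper end rests on an outcome driven by gender, which is the case least favourable to the SAP. The estimate stays unbiased throughout.

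The models affected are exploratory and carry no significance threshold, so a change of this order would not alter a reading of size and direction. The feasibility, acceptability, engagement and by-arm descriptive summaries do not use the stratum. No change to the plan is needed.
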